Functional outcome: modified Rankin Scale to assess dependency at 6 and 12 months. If participants are unable to be contacted, the central assessor will obtain the most recent modified Rankin Score from the local staff (if available).

Cognitive outcomes: Telephone MOCA, Telephone Interview for Cognitive Status (TICS), mobility and physical functioning sections of the Stroke Impact Scale and the ZUNG will be collected remotely at six and 12 months by the central trial team. TRAILS B will be repeated when attending for 1 year MR in Centres that are able to do this. TICS will be collected for consistency with prior and ongoing trials (ENOS, TARDIS, RIGHT 2, TICH) and good comparability.⁶² TMOCA will be collected for comparison with TICS for potential use in future trials as it purports to assess executive function more than TICS. IQCODE will be collected from the relative/partner/carer by post or phone.

Health economics: EQ-5D-5L, EQ-VAS, return to work, hospitalisation, need for long term supportive care will be collected at 12 months.

Follow-up Brain MRI: all patients will have repeat brain MRI at 12 months to assess burden of WMH, microbleeds, lacunes, new infarcts or haemorrhage and atrophy and where feasible to assess diffusion tensor tissue parameters. These scans will be sent to Edinburgh for central blinded adjudication.

Follow-up at 6 and 12 months will be by post and telephone, blinded to allocated treatment. A trained assessor who is part of the central trial team and based either at the University of Edinburgh or University of Nottingham and who is blinded to treatment and baseline clinical information, will first confirm with the GP that the participant is contactable. They will then contact the patient or carer by post and phone to administer the questionnaires following a standardised script.

In addition to the assessments detailed above, participants will receive one to five informal contacts over the duration of their trial participation. One will consist of a participant newsletter and any other informal contacts will be a brief phone call or additional participant newsletter. During those contacts, a member of the central or site teams will update participants on the trial status, thank them for their continued help with the study, and give them an opportunity to ask questions.

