8 DATA COLLECTION

Please see section 7.2 above for measurements and time points.

The medical history, cognitive assessment, and structured questionnaire for symptoms and adverse events will be obtained from the patient in person (and medical notes where necessary) and by telephone by the study researcher after appropriate training as required and entered into the electronic case record form. These researchers will also measure blood pressure, obtain blood samples for haematology and biochemistry as necessary (analysed in the hospital NHS haematology or biochemistry labs in the centre in which the patient has been recruited).

The researcher at each site will co-ordinate the appointment for one year MRI. A reminder that the MRI appointment is due will be sent by the Trial Co-ordinating Centre. The MRI will be performed in approved radiology departments using sequences specified for the trial.

All baseline medical, cognitive, scanning and laboratory data will be entered into a secure password protected electronic case record form (eCRF) run from the University of Nottingham, accessible to approved research staff for data entry. The data from central reading of MRI will be added to the eCRF data for statistical analysis. Participant and relative/carer contact details, required to perform Trial follow-up, will be stored in an encrypted secure password-protected database also provided by the University of Nottingham, separate to the Trial eCRF database, and only accessible to selected researchers in the Trials Unit, University of Edinburgh and the University of Nottingham.

Paper versions of the CRF (i.e. source data sheet) will be available to assist with data collection when interviewing patients at baseline and during follow-up visits in phone or in person. Paper CRFs will be filed in the patient's paper-based folder and held in a secure locked filing cabinet at site.

The MR or CT brain images obtained at diagnosis of the stroke and 1 year follow-up MRI will be anonymised and sent to Edinburgh where they will be assessed and quantified for the index stroke, features of small vessel disease and other features, using validated scores and volume measurements by an experienced rater. Images will only be identified by study ID.

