9.2 PROPOSED ANALYSES

We will compare cilostazol v no cilostazol, ISMN v no ISMN, cilostazol and ISMN v neither. The proportion completing to target dose and any adverse events will be assessed using odds ratios. The LACI-2 will focus on numbers recruited, retained, tolerance and safety outcomes, blinded for TSC and unblinded intention to treat (ITT) for DMC. Safety analysis will use: Kaplan-Meier and Cox proportional regression for analysis of time-to-event outcomes of death; binary logistic regression for SAEs, recurrent stroke, MI, and in those completing 12 month MRI, the amount of microbleeds, siderosis, new infarcts, WMH burden; all adjusted for minimisation variables to maximise power.⁶⁷ We will collect data for future health economics analysis (EQ-5D-5L, EQ-VAS).

A secondary ITT analysis will be performed using logistic regression adjusted for minimisation variables of cilostazol+/-ISMN versus control on efficacy and safety outcomes, with secondary tests of subgroup interactions. Ordinal logistic regression will be used for ordinal categorical outcomes (e.g. mRS) to increase power.⁶⁸

A Statistical Analysis Plan (SAP) will be published prior to database lock and will describe analysis procedures and procedures for missing, unused or spurious data, and definitions of populations analysed.

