- Death, including fatal haemorrhage, aiming for less than outside the upper 95% CI of 2% per year.
- The *combined rate* of recurrent stroke, MI, death, cognitive impairment and dependency, aiming for 40-50% at one year after enrolment.

Comparison of rates of events between the treatment groups: cilostazol vs no cilostazol, ISMN vs no ISMN, and cilostazol and ISMN vs neither, for:

- Systemic or intracranial bleeding, recurrent cerebral and systemic vascular events, and vascular and non-vascular causes of death.
- Death, all cause.
- New ischaemic or haemorrhagic stroke lesion or increase in SVD lesions on MRI.
- Composite of: recurrent clinically-evident stroke, MI, death, cognitive impairment (including dementia) and dependency.
- Individual event: stroke (clinically-evident or imaging-detected ischaemic or haemorrhagic stroke to be reported separately), TIA, myocardial ischaemia, cognitive impairment and dementia.
- New infarcts and haemorrhages, absolute and change in WMH, microhaemorrhages, lacunes, atrophy imaging variables from central read of baseline imaging and one year MRI
- The comparisons of combined cilostazol and ISMN versus neither, whilst being very underpowered statistically, are presented since these may be the two groups studied in the planned follow-on trial.

Central tendency, comparisons and regressions will be analysed as follows (**Table D**).

Table D. Descriptive and analytical statistics

	Binary	Nominal	Ordinal	Continuous
Central tendency and distribution	N (%)	N (%)	Median [interquartile range]	Mean (standard deviation)
Comparisons	Chi-square (2x2)	Chi-square (2x2, or rxc)	Mann-Whitney U or Kruskal-Wallis	t-test (pooled) or 1-way ANOVA
Regression	Binary logistic regression (BLR)	-	Ordinal logistic regression (OLR)	Multiple linear regression (MLR)

27b Covariate adjustment: Analyses will be adjusted for minimisation covariates:

- Age, sex, stroke severity (NIHSS), dependency resulting from the stroke, systolic blood pressure, smoking status, time after stroke, years of education.

Covariate adjustment with continuous variables (age, NIHSS, SBP, time after stroke, years of education) will use original, not dichotomised, data.

27c Assumption checking: The assumption of proportionality will be tested using the likelihood test.

27d Alternative methods: If the data fail the assumption of proportionality (tested using the likelihood test), we will use alternative methods such as multiple logistic regression.

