No. microhaemorrhages (%)										
1	XX	XX (X)	XX (X)	XX (X)	XX (X)	XX (X)	XX (X)	XX (X)	XX (X)	XX (X)
2	XX	XX (X)	XX (X)	XX (X)	XX (X)	XX (X)	XX (X)	XX (X)	XX (X)	XX (X)
3	XX	XX (X)	XX (X)	XX (X)	XX (X)	XX (X)	XX (X)	XX (X)	XX (X)	XX (X)
4	XX	XX (X)	XX (X)	XX (X)	XX (X)	XX (X)	XX (X)	XX (X)	XX (X)	XX (X)
>= 5	XX	XX (X)	XX (X)	XX (X)	XX (X)	XX (X)	XX (X)	XX (X)	XX (X)	XX (X)
Type of microhaemorrhages (%)										

	N	All	ISMN	No ISMN	Cil	No Cil	ISMN + Cil	ISMN only	Cil only	None
Lobar	XX	XX (X)	XX (X)	XX (X)	XX (X)	XX (X)	XX (X)	XX (X)	XX (X)	XX (X)
Deep	XX	XX (X)	XX (X)	XX (X)	XX (X)	XX (X)	XX (X)	XX (X)	XX (X)	XX (X)
Both	XX	XX (X)	XX (X)	XX (X)	XX (X)	XX (X)	XX (X)	XX (X)	XX (X)	XX (X)
Superficial siderosis present	XX	XX (X)	XX (X)	XX (X)	XX (X)	XX (X)	XX (X)	XX (X)	XX (X)	XX (X)
Siderosis focal	XX	XX (X)	XX (X)	XX (X)	XX (X)	XX (X)	XX (X)	XX (X)	XX (X)	XX (X)
Siderosis disseminated	XX	XX (X)	XX (X)	XX (X)	XX (X)	XX (X)	XX (X)	XX (X)	XX (X)	XX (X)
Siderosis location										
Left	XX	XX (X)	XX (X)	XX (X)	XX (X)	XX (X)	XX (X)	XX (X)	XX (X)	XX (X)
Right	XX	XX (X)	XX (X)	XX (X)	XX (X)	XX (X)	XX (X)	XX (X)	XX (X)	XX (X)
Both	XX	XX (X)	XX (X)	XX (X)	XX (X)	XX (X)	XX (X)	XX (X)	XX (X)	XX (X)
Atrophy										
Brain tissue volume reduction	XX	XX (X)	XX (X)	XX (X)	XX (X)	XX (X)	XX (X)	XX (X)	XX (X)	XX (X)
Central brain tissue volume										
Modest	XX	XX (X)	XX (X)	XX (X)	XX (X)	XX (X)	XX (X)	XX (X)	XX (X)	XX (X)
Severe	XX	XX (X)	XX (X)	XX (X)	XX (X)	XX (X)	XX (X)	XX (X)	XX (X)	XX (X)
Cortical brain tissue volume										
Modest	XX	XX (X)	XX (X)	XX (X)	XX (X)	XX (X)	XX (X)	XX (X)	XX (X)	XX (X)
Severe	XX	XX (X)	XX (X)	XX (X)	XX (X)	XX (X)	XX (X)	XX (X)	XX (X)	XX (X)
White Matter hyperintensities (%)										
White matter hyperintensities	XX	XX (X)	XX (X)	XX (X)	XX (X)	XX (X)	XX (X)	XX (X)	XX (X)	XX (X)
Anterior white matter lucency										
Restricted region adjoining ventricles	XX	XX (X)	XX (X)	XX (X)	XX (X)	XX (X)	XX (X)	XX (X)	XX (X)	XX (X)
Covering ventricle to cortex	XX	XX (X)	XX (X)	XX (X)	XX (X)	XX (X)	XX (X)	XX (X)	XX (X)	XX (X)
Posterior white matter lucency										
Restricted region adjoining ventricles	XX	XX (X)	XX (X)	XX (X)	XX (X)	XX (X)	XX (X)	XX (X)	XX (X)	XX (X)
Covering ventricle to cortex	XX	XX (X)	XX (X)	XX (X)	XX (X)	XX (X)	XX (X)	XX (X)	XX (X)	XX (X)
Anterior and/or Posterior white matter lucency										

	N	All	ISMN	No ISMN	Cil	No Cil	ISMN + Cil	ISMN only	Cil only	None

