Stopped normal activities	xx (xx.x)	xx (xx.x)	(xx.x, xx.x), p=0.xxx	xx (xx.x)	xx (xx.x)	(xx.x, xx.x), p=0.xxx	xx (xx.x)	xx (xx.x)	(xx.x, xx.x), p=0.xxx
Nausea	xx (xx.x)	xx (xx.x)	(xx.x, xx.x), p=0.xxx	xx (xx.x)	xx (xx.x)	(xx.x, xx.x), p=0.xxx	xx (xx.x)	xx (xx.x)	(xx.x, xx.x), p=0.xxx
Stopped normal activities	xx (xx.x)	xx (xx.x)	(xx.x, xx.x), p=0.xxx	xx (xx.x)	xx (xx.x)	(xx.x, xx.x), p=0.xxx	xx (xx.x)	xx (xx.x)	(xx.x, xx.x), p=0.xxx
Bleeding	xx (xx.x)	xx (xx.x)	(xx.x, xx.x), p=0.xxx	xx (xx.x)	xx (xx.x)	(xx.x, xx.x), p=0.xxx	xx (xx.x)	xx (xx.x)	(xx.x, xx.x), p=0.xxx
Stopped normal activities	xx (xx.x)	xx (xx.x)	(xx.x, xx.x), p=0.xxx	xx (xx.x)	xx (xx.x)	(xx.x, xx.x), p=0.xxx	xx (xx.x)	xx (xx.x)	(xx.x, xx.x), p=0.xxx
Bruising	xx (xx.x)	xx (xx.x)	(xx.x, xx.x), p=0.xxx	xx (xx.x)	xx (xx.x)	(xx.x, xx.x), p=0.xxx	xx (xx.x)	xx (xx.x)	(xx.x, xx.x), p=0.xxx
Stopped normal activities	xx (xx.x)	xx (xx.x)	(xx.x, xx.x), p=0.xxx	xx (xx.x)	xx (xx.x)	(xx.x, xx.x), p=0.xxx	xx (xx.x)	xx (xx.x)	(xx.x, xx.x), p=0.xxx
Falls	xx (xx.x)	xx (xx.x)	(xx.x, xx.x), p=0.xxx	xx (xx.x)	xx (xx.x)	(xx.x, xx.x), p=0.xxx	xx (xx.x)	xx (xx.x)	(xx.x, xx.x), p=0.xxx
Stopped normal activities	xx (xx.x)	xx (xx.x)	(xx.x, xx.x), p=0.xxx	xx (xx.x)	xx (xx.x)	(xx.x, xx.x), p=0.xxx	xx (xx.x)	xx (xx.x)	(xx.x, xx.x), p=0.xxx

Table 9. Adjudicated 1 year MRI imaging characteristics by randomised group: isosorbide mononitrate (ISMN), cilostazol (Cil) and both together.

Data are number (%), median [IQR], or mean (standard deviation).

	N	All	OR/MD/ p- value				OR/MD/ p- value				ISMN + Cil		OR/MD/ p- value	
			ISMN	No ISMN	HR (95%CI)		Cil	No Cil	HR (95%CI)		None	(95%CI)		
Patients randomised	XX	XX	XX	XX			XX	XX			XX	XX		
Scan														
Time to scan (days)	XX	XX (X)	XX (X)	XX (X)	MLR	XX	XX (X)	XX (X)	MLR	XX	XX (X)	XX (X)	MLR	XX
Scan quality (%)													OLR	XX
Good	XX	XX (X)	XX (X)	XX (X)			XX (X)	XX (X)			XX (X)	XX (X)		
Moderate	XX	XX (X)	XX (X)	XX (X)			XX (X)	XX (X)			XX (X)	XX (X)		
Poor	XX	XX (X)	XX (X)	XX (X)			XX (X)	XX (X)			XX (X)	XX (X)		
Appearance of the index infarct now (%)														
Completely cavitated - visible on T2, FLAIR and T1"	XX	XX (X)	XX (X)	XX (X)	BLR	XX	XX (X)	XX (X)	BLR	XX	XX (X)	XX (X)	BLR	XX
Partially cavitated - lacy	XX	XX (X)	XX (X)	XX (X)	BLR	XX	XX (X)	XX (X)	BLR	XX	XX (X)	XX (X)	BLR	XX
Partially cavitated - hole + large WMH rim	XX	XX (X)	XX (X)	XX (X)	BLR	XX	XX (X)	XX (X)	BLR	XX	XX (X)	XX (X)	BLR	XX

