Partially cavitated - FLAIR cavity but not=CSF	XX	XX (X)	XX (X)	XX (X)	BLR	XX	XX (X)	XX (X)	BLR	XX	XX (X)	XX (X)	BLR	XX
Partially cavitated - FLAIR=WMH T2=cavity	XX	XX (X)	XX (X)	XX (X)	BLR	XX	XX (X)	XX (X)	BLR	XX	XX (X)	XX (X)	BLR	XX
Partially cavitated - visible on T2 not FLAIR	XX	XX (X)	XX (X)	XX (X)	BLR	XX	XX (X)	XX (X)	BLR	XX	XX (X)	XX (X)	BLR	XX
Not cavitated (WML-like)	XX	XX (X)	XX (X)	XX (X)	BLR	XX	XX (X)	XX (X)	BLR	XX	XX (X)	XX (X)	BLR	XX
Disappeared	XX	XX (X)	XX (X)	XX (X)	BLR	XX	XX (X)	XX (X)	BLR	XX	XX (X)	XX (X)	BLR	XX
Become visible	XX	XX (X)	XX (X)	XX (X)	BLR	XX	XX (X)	XX (X)	BLR	XX	XX (X)	XX (X)	BLR	XX
Never visible	XX	XX (X)	XX (X)	XX (X)	BLR	XX	XX (X)	XX (X)	BLR	XX	XX (X)	XX (X)	BLR	XX
Evidence of new stroke (%)														

	N	All	OR/MD/ p- value			OR/MD/ p- value			ISMN + Cil		OR/MD/ p- value	
			ISMN	No ISMN	(95%CI)	Cil	No Cil	(95%CI)	None	(95%CI)		
Ischaemic	XX	XX (X)	XX (X)	XX (X)	BLR XX	XX (X)	XX (X)	BLR XX	XX (X)	XX (X)	BLR	XX
Haemorrhagic	XX	XX (X)	XX (X)	XX (X)	BLR XX	XX (X)	XX (X)	BLR XX	XX (X)	XX (X)	BLR	XX
Microhaemorrhages (%)	XX	XX (X)	XX (X)	XX (X)	BLR XX	XX (X)	XX (X)	BLR XX	XX (X)	XX (X)	BLR	XX
No. microhaemorrhages (%)					OLR XX			OLR XX			OLR	XX
1	XX	XX (X)	XX (X)	XX (X)		XX (X)	XX (X)				XX (X)	XX (X)
2	XX	XX (X)	XX (X)	XX (X)		XX (X)	XX (X)				XX (X)	XX (X)
3	XX	XX (X)	XX (X)	XX (X)		XX (X)	XX (X)				XX (X)	XX (X)
4	XX	XX (X)	XX (X)	XX (X)		XX (X)	XX (X)				XX (X)	XX (X)
>= 5	XX	XX (X)	XX (X)	XX (X)		XX (X)	XX (X)				XX (X)	XX (X)
Change from baseline	XX	XX [XX, XX]	XX [XX, XX]	XX [XX, XX]	OLR XX	XX [XX, XX]	XX [XX, XX]	OLR XX	XX [XX, XX]	XX [XX, XX]	OLR	XX
Small vessel disease score												
Total	XX	XX [XX, XX]	XX [XX, XX]	XX [XX, XX]	OLR XX	XX [XX, XX]	XX [XX, XX]	OLR XX	XX [XX, XX]	XX [XX, XX]	OLR	XX
Change from baseline	XX	XX [XX, XX]	XX [XX, XX]	XX [XX, XX]	OLR XX	XX [XX, XX]	XX [XX, XX]	OLR XX	XX [XX, XX]	XX [XX, XX]	OLR	XX
Atrophy												
Brain tissue volume reduction	XX	XX (X)	XX (X)	XX (X)	BLR XX	XX (X)	XX (X)	BLR XX	XX (X)	XX (X)	BLR	XX
Central brain tissue volume					OLR XX			OLR XX			OLR	XX
Modest	XX	XX (X)	XX (X)	XX (X)		XX (X)	XX (X)				XX (X)	XX (X)
Severe	XX	XX (X)	XX (X)	XX (X)		XX (X)	XX (X)				XX (X)	XX (X)
Cortical brain tissue volume					OLR XX			OLR XX			OLR	XX
Modest	XX	XX (X)	XX (X)	XX (X)		XX (X)	XX (X)				XX (X)	XX (X)
Severe	XX	XX (X)	XX (X)	XX (X)		XX (X)	XX (X)				XX (X)	XX (X)
Change from baseline					OLR XX			OLR XX			OLR	XX

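### Protocol 9.2 names siderosis as a 12-month MRI safety outcome, but the SAP plans no one-year siderosis comparison; the planned volume measurements also have no stated analysis

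*Protocol*

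**What the plan says.** For the safety analysis in patients who complete the 12-month MRI, protocol section 9.2 plans binary logistic regression for "the amount of microbleeds, siderosis, new infarcts, WMH burden; all adjusted for minimisation variables to maximise power". Protocol section 7.2 describes the purpose of the 12-month scan as "to assess burden of WMH, microbleeds, lacunes, new infarcts or haemorrhage and atrophy"; siderosis is not in that list. Protocol section 8 says that the diagnostic and one-year scans will be assessed and quantified "using validated scores and volume measurements by an experienced rater".

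In the SAP, baseline Table 5 has a row "Superficial siderosis present", followed by rows for type (focal, disseminated) and side. The one-year table is Table 9, titled "Adjudicated 1 year MRI imaging characteristics by randomised group". It has no siderosis row and no row for a measured volume. The imaging item in section 27a covers new infarcts and haemorrhages and "absolute and change in WMH, microhaemorrhages, lacunes, atrophy imaging variables from central read"; it names no scale for WMH and does not mention siderosis. Section 27b keeps the adjustment for minimisation variables. Section 4c says that the SAP prevails where it differs from the protocol.

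**The concern.** Cilostazol is given on top of guideline antiplatelet treatment, and protocol section 1.2 names added bleeding as a safety question. Haemorrhagic change on MRI is part of the safety endpoint in both documents, with its own significance level of 0.01. A marker of past bleeding that is read at baseline, and that the protocol names for comparison at one year, should appear in the one-year table. As written it does not, and the SAP gives no reason.

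Volumes raise a smaller version of the same problem. They are to be measured, but no model or table uses them. If they are analysed later, the scale and model for WMH change will be chosen after the data are available, and preventing that is the SAP's stated purpose.

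**Working it through.** Neither document states a power, effect size, standard deviation or event rate for any MRI outcome, so there is no figure of the plan's own to reproduce. The check is mainly a comparison of places.

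**1. Siderosis, place by place**

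| Place | Siderosis |
|---|---|
| Protocol 9.2, 12-month MRI analyses | Named |
| Protocol 7.2, purpose of 12-month MRI | Not listed |
| SAP Table 5, baseline imaging | Presence, type and side |
| SAP 27a, comparisons between groups | Not named |
| SAP Table 9, one-year imaging | No row |
| SAP figure list, items 5 and 9 | Item 5 follows Table 9; item 9 names infarct or haemorrhage, WMH, microbleeds and atrophy |
| SAP 4a, changes from version 1.4 to 1.5 | No removal recorded (earlier revisions are not listed) |
| SAP 4c | SAP overrides protocol |

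The comparison in protocol 9.2 therefore has no counterpart in the document that governs the analysis.

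**2. Bleeding markers that remain in Table 9.** These are new haemorrhagic stroke, microhaemorrhage presence, number and change from baseline, and probable old haemorrhage. None of them records siderosis.

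**3. How much a siderosis row could show.** Protocol 9.1 expects at least 15% to miss the repeat MRI: 400 × 0.85 = 340 scanned, or 170 per arm for each drug. With the 363 recruits shown in SAP Table 2, 363 × 0.85 ≈ 309. The prevalence is not given, so 1%, 2% and 5% are assumed:

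| Assumed prevalence, both arms | Cases in 340 | Cases in 309 | Power for a doubling, α = 0.05 | Power for a doubling, α = 0.01 |
|---|---|---|---|---|
| 1% | 3.4 | 3.1 | 11% | 3% |
| 2% | 6.8 | 6.2 | 19% | 7% |
| 5% | 17 | 15.4 | 42% | 20% |

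Power is Φ[(|p1 − p2| − z·√(2p̄(1 − p̄)/n)) / √((p1(1 − p1) + p2(1 − p2))/n)], with n = 170 per arm, two-sided and unadjusted. For 2% against 4%: (0.02 − 1.96 × 0.0185)/0.0185 = −0.88, which gives 19%. A logistic model with treatment and eight minimisation variables has at least nine terms, so 17 cases leave 17/9 ≈ 1.9 per term and 3.4 cases leave about 0.4. Full adjustment is unlikely to be workable.

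**4. Volumes.** Protocol 8 plans the measurement. Protocol 9.2 plans only WMH burden, by binary logistic regression. Table 9 covers WMH by presence, Fazekas grade, change in grade, overall change and five regional More/Less/No Change ratings. It covers atrophy by presence and by modest or severe grade. The measured volumes enter no analysis.

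**5. Level 0.** In Table 9 the "No. microhaemorrhages" block runs from 1 to ≥5, lacunes from 1 to ≥5 and Fazekas grade from 1 to 3, all by ordinal regression. Each block also has a presence row by binary logistic regression and a change row. Table 5 uses the same display. The SAP does not say whether patients at level 0 enter the ordinal models.

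**The case against.** The best defence is that this is a feasibility trial, the MRI comparisons were never powered, several bleeding markers remain, and siderosis might be thought to fall under new haemorrhagic lesions. The first three points stand and limit the importance of the gap. The last does not: the SAP gives no such definition, and the haemorrhagic row in Table 9 sits under new stroke. Protocol 7.2 also omits siderosis from the 12-month list, but that does not cancel section 9.2.

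Two stronger readings are tempting, and the documents support neither.

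A reader might infer that, because the count rows start at 1, new microbleed carriers would go unseen. The SAP never says that zeros are excluded, and the presence row and change row cover new carriers. As an illustration, assume that carriers rise from 25% to 40% with 154 scanned per arm (309/2). The unadjusted presence test has power Φ[(0.15 − 1.96 × 0.0534)/0.0527] = Φ(0.86) ≈ 81% at 0.05. At 0.01 it is Φ[(0.15 − 2.576 × 0.0534)/0.0527] ≈ 59%.

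A reader might also infer that the protocol promised a volume analysis and that the SAP replaced it with a much weaker one. Protocol 9.2 promises no volume analysis. Its method is binary, and its remark on power refers to covariate adjustment, which SAP 27b keeps. Any loss against volumes depends on distributions that neither document gives. Protocol 9.1 itself cites the short-term variance of WMH change as a reason for similar or larger sample sizes. Patients with only a baseline CT would have no MRI volume to compare.

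**Conclusion.** The siderosis gap is established from the text: named in protocol 9.2, read at baseline, and absent from every one-year comparison in the SAP, which prevails. One bleeding marker would go unreported between arms. The consequence is incomplete safety reporting, not a wrong conclusion on the primary endpoint. On the assumed prevalences the comparison would rest on about 3 to 17 cases and could not establish safety alone.

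The volume point is secondary: a planned measurement without a planned analysis, and a benefit of unknown size. Level 0 needs clarification only. The conclusion rests on Table 9, section 27a and the figure list as they stand in SAP version 1.5.

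**What to change.** Before the database is locked:

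- Add two rows to Table 9: superficial siderosis at one year, and siderosis new since baseline in patients with a baseline MRI. Analyse both by binary logistic regression adjusted for the minimisation variables where event numbers allow; otherwise give counts with exact confidence intervals. Name siderosis in section 27a and figure item 9, or state why it was removed.
- Add one-year WMH volume (log scale) and brain volume by linear regression on baseline volume, scan interval and minimisation variables, in patients with a baseline MRI. Keep the visual grade rows for the rest.
- State that level 0 is included in the ordinal models for microhaemorrhages, lacunes and Fazekas grade.

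The cost is four table rows and a sentence, provided that the central reading already records one-year siderosis and volumes. The documents do not show the reading form. If siderosis was not captured at one year, those scans would need a further read.
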